#### **10.1.3 Demographic and Baseline Characteristics**

Patient demographic and baseline characteristics, including age, gender, medical history, and prior therapy, will be summarized using descriptive statistics. For continuous variables, descriptive statistics (number [n], mean, standard deviation, standard error, median (range) will be provided. For categorical variables, patient counts and percentages will be provided.

#### **10.1.4 Efficacy Analysis**

A primary activity endpoint is not defined for the Phase I study. The primary activity endpoint for the Phase II study is response rate. Response rates (overall, clinical benefit) and depth of response will be calculated as the percent of evaluable patients that have confirmed sCR/CR/VGPR or PR (overall) or sCR/CR/VGPR/PR/MR or SD (clinical benefit), exact 95% confidence intervals will be calculated for these estimates. Response rates will also be evaluated

based on number and type of prior therapy(ies). Response defined as per modified IMWG criteria. Time to response, duration of response, and survival (overall and progression-free) will be estimated using the product-limit method of Kaplan and Meier.

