**Phase II:**

The primary objective is to estimate the response rate and to evaluate the antitumor activity of the three drug combination: MLN9708 (at the RP2D), pomalidomide, and dexamethasone, in patients with relapsed or relapsed/refractory multiple myeloma. The primary endpoint is a confirmed tumor response of sCR/CR/VGPR or PR and is based on IMWG Criteria. A single cycle of treatment will be given in a 28 day cycle. Each patient's disease status will be evaluated at baseline. Response will be assessed at the end of each cycle/just prior to the start of each cycle and is based on the IMWG criteria.

**Statistics/Sample Size and Accrual:** The phase II portion of this study will implement a Gehan two-stage design to estimate the response rate and to evaluate the activity of MLN9708 when given in combination with pomalidomide and dexamethasone (Gehan 1961). The phase II portion of the study is expected to enroll a minimum of 9 and a maximum of 25 patients. The six patients treated at the RP2D in the phase I portion of the study will count toward the 25 patients required; given this, we expect to enroll only 19 new patients on the phase II trial. The sample size is based on the desire to estimate the response rate with at most 10% standard error, and early stopping if the combination is unexpectedly ineffective.

At stage 1, 9 patients will be entered on the study. If 0 responses are seen in the first 9 patients treated, the study will be terminated and the true regimen response will be declared  $\leq 30\%$ . If at least 1 patient responds, the trial will continue to the second stage. Because patients treated during the phase I portion of the trial at the dose selected for the phase II trial will be counted ( $n=6$ ), only 3 additional patients will be enrolled at stage 1. Under this design if the study regimen is  $>30\%$  effective, there would be  $\sim 95.6\%$  chance of at least one success.

At stage 2, 16 additional patients will be entered. This accrual provides for estimation of the response rate with no more than 10% standard error.

**Analysis:** The overall response rate will be calculated as the percent of evaluable patients that have confirmed sCR/CR/VGPR or PR; the clinical benefit response rate will be calculated as the percent of evaluable patients that have confirmed sCR/CR/VGPR/PR/ MR or SD; exact

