95% confidence intervals will be calculated for these estimates. Response rates will also be evaluated based on number and type of prior therapy(ies). Time to response, duration of response, and survival will be estimated using the product-limit method of Kaplan and Meier.

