**Phase II:**

The primary activity endpoint is response rate (confirmed sCR/CR/VGPR or PR), based on the International Myeloma Working Group (IMWG) criteria, calculated as the number of responders divided by the number of evaluable patients. Confirmation of sCR/CR/VGPR or PR assessed by IMWG criteria.

Secondary activity endpoints for this study are as follows:

- Duration of response, defined as the time interval from the date of first documented response (sCR/CR/VGPR or PR) to documented disease relapse, progression or death whichever occurs first.
- Clinical benefit response, based on the International Myeloma Working Group (IMWG) criteria, calculated as the number of responders plus those with a minimal response (MR) or stable disease (SD) divided by the number of evaluable patients. Confirmation of sCR/CR/VGPR/PR/MR or SD assessed by IMWG criteria.
- Overall survival, defined as the time interval from date of first dose of study drug to date of death from any cause.
- Progression-free survival, defined as the time interval from date of first dose of study drug to first documented disease relapse, progression or death from any cause, whichever occurs first.

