### 4.3 Duration of Study

Accrual, for both phases, is expected to be completed in 26 months; with approximately 2 patients enrolled each month. Patients will be treated in 28-day treatment cycles until disease relapse, progression or unacceptable toxicity, withdrawal of consent, or protocol specified parameters to stop treatment. Patients who discontinue study treatment for reasons other than disease relapse/progression will continue to have disease assessments per International Myeloma Working Group (IMWG) criteria until relapse or progression, initiation of new

anticancer treatment, or death whichever occurs first. Patients will be followed to collect further anticancer treatment and survival information until death, loss to follow-up, withdrawal of consent, study termination or up to 24 months post treatment.

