## 10. STATISTICAL AND QUANTITATIVE ANALYSES

### 10.1 Statistical Methods

#### 10.1.1 Determination of Sample Size

**Phase I:** The phase I study will follow a 3+3 design, to evaluate toxicities associated with MLN9708 when given in combination with pomalidomide and dexamethasone. Two doses of MLN9708 (dose level -1 and dose level 1: 3 mg; dose level 2: 4 mg) will be tested in up to three possible dose levels; there will be no dose reductions below the 3mg dose of MLN9708. In the phase I portion of this study, the total sample size will depend on the number of dose levels evaluated to determine the maximum tolerated dose (MTD). While the phase I study is expected to enroll and treat 9 patients (3 patients treated on dose level 1 and 6 additional patients treated at dose level 2 -assuming the 4mg dose is well tolerated), a maximum of 18 patients could be treated (6 patients per dose level). The highest dose level that produces  $\leq 1/6$  DLTs in cycle 1 will be the MTD. (See section 7.4 for dose expansion/escalation rules.) The recommended phase II dose (RP2D) of MLN9708 and pomalidomide will generally be the MTD, but it may be less than the MTD based on a review of available data/cumulative toxicities from phase I.

**Phase II:** For this trial, where MLN9708 will be added to pomalidomide and dexamethasone, patients with prior exposure to either of these agents would not be excluded, unlike the patients treated on the randomized phase III study of comparing pomalidomide plus dexamethasone, to high-dose dexamethasone alone. As many patients (>50%) are likely to have been previously treated with one or both of these agents we consider a response rate of 30% sufficient efficacy to justify further development. In addition, the estimation of response in this refractory/high-risk population is of equal importance. Given this, the phase II portion of the trial, will use a Gehan two stage design (Gehan, 1961). The phase II trial is expected to enroll a minimum of 9 and a maximum of 25 patients. The six patients treated at the RP2D in the phase I portion of the study will count toward the 25 patients required. Given this, we expect to enroll only 19 new patients on the phase II trial. The sample size is based on the desire to estimate the response rate with at most 10% standard error, and early stopping if the combination is unexpectedly ineffective. The primary endpoint is confirmed tumor response (sCR/CR/VGPR or PR).

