#### **10.1.2 Populations for Analysis**

**Phase I (Evaluable for Toxicity):** Patients will be considered evaluable for toxicity if they receive any study drug. Patients will be considered evaluable for dose limiting toxicity if they receive at least 75% of both Pomalidomide and MLN9708 and are followed for the full 28 days during cycle 1 or experience a DLT. All patients who are not evaluable for dose limiting toxicity will be replaced.

**Phase II (Evaluable for Toxicity):** Patients will be considered evaluable for toxicity if they receive any study drug. Patients in Phase II will not be replaced based on toxicity.

**Phase I and II (Evaluable for Response):** For the phase II portion, as part of the primary analysis, patients will be considered evaluable for response if they are eligible, have baseline disease assessments, and receive any protocol treatment. As part of a secondary analysis, patients will be considered evaluable for response if they have baseline disease assessments, receive at least 75% of both Pomalidomide and MLN9708 during the first cycle of therapy and have had their disease re-evaluated. Patients will have their response classified according to the IMWG response criteria. All patients in phase II and those treated at the RP2D in phase I, who are not evaluable for response will be replaced.

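### Time to response is planned by Kaplan-Meier with no origin, analysis set or rule for patients who progress, die or start new therapy first; cumulative incidence would close the gap

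*Combined protocol and SAP*

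**What the plan says.** Section 10.1.4 (Efficacy Analysis) covers time to response in one sentence: "Time to response, duration of response, and survival (overall and progression-free) will be estimated using the product-limit method of Kaplan and Meier". The Phase II statistical paragraph of the Protocol Summary has the shorter form: "Time to response, duration of response, and survival will be estimated using the product-limit method of Kaplan and Meier". Both copies of the protocol text in the combined file read the same way.

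Section 3.1 defines duration of response, overall survival and progression-free survival, each with a start date and its events. Time to response is not defined there, and it is not among the phase II objectives in Section 2.2.

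The primary response rate is a separate quantity, "calculated as the number of responders divided by the number of evaluable patients". Under Section 10.1.2 patients enter its primary analysis if "they are eligible, have baseline disease assessments, and receive any protocol treatment". No post-baseline assessment is required, so early progressors and early deaths stay in the denominator.

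Section 4.3 fixes when response can still be observed: "Patients will be treated in 28-day treatment cycles until disease relapse, progression or unacceptable toxicity". For patients who stop for other reasons, disease assessments run until relapse or progression, the start of new "anticancer treatment, or death whichever occurs first".

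**The concern.** Death is an event in all three defined time-to-event endpoints, and progression is an event in two of them (duration of response and PFS). Neither is left as a competing event, so Kaplan-Meier suits all three. Time to response differs: progression, death or new therapy ends the chance of a first response on study.

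The product-limit method has no category for such events. The usual default is to censor the patient on that date, which assumes that the patient would have gone on to respond at the same rate as those still at risk. One minus Kaplan-Meier then estimates response in a hypothetical setting without progression or death, and lies above the proportion who actually respond.

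At stake is a descriptive figure. A report could carry a response rate and a time-to-response curve from the same patients that imply different chances of responding. Because the plan is silent, the choice between analyses could also be made after the data are seen.

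**Working it through.** **The plan's own figure.** The plan states no number for time to response. The nearest is the standard error of the response rate, given as at most 10%. With √(p(1−p)/n) at its maximum, p = 0.5 and n = 25: √(0.25/25) = 0.100. This reproduces, and serves below only as a yardstick.

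**Inputs from the documents.** Final size: "The six patients treated at the RP2D in the phase I portion of the study will count toward the 25 patients required". Assessment interval: "Response will be assessed at the end of each cycle/just prior to the start of each cycle", with 28-day cycles. Target response rate: 30% (Section 10.1.1).

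**Assumed inputs.** All response and progression times, because the documents give none for this regimen.

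**Step 1: one worked example.** Take 8 responders in 25 (32%). Responses occur at cycles 1, 1, 1, 2, 2, 3, 4, 6. The 17 non-responders progress or die at cycles 1, 1, 2, 2, 2, 3, 3, 3, 4, 4, 5, 5, 6, 7, 8, 9, 10 and are censored there. The numbers at risk at the response times are 25, 20, 15, 11 and 6.

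Kaplan-Meier = (22/25)(18/20)(14/15)(10/11)(5/6) = 0.56, so 1 − KM = 44%, against 32% who responded.

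**Step 2: cumulative incidence on the same data.** Each increment is (probability still event-free) × (responses / at risk). With no other censoring this is (n_at-risk/25) × (d/n_at-risk) = d/25. The sum is (3+2+1+1+1)/25 = 8/25 = 32%, equal to the crude rate.

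**Step 3: simulated trials of 25.** Responses fall in cycles 1 to 6 with probabilities 0.35, 0.30, 0.15, 0.10, 0.05, 0.05. Non-responders leave uniformly over the stated cycles and are censored there. The table gives the mean final 1 − KM over 4,000 trials, with the excess over the crude rate in brackets.

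| Crude rate | Leave over cycles 1–6 | 1–12 | 1–24 |
|---|---|---|---|
| 8/25 = 32% | 46.4% (+14.4) | 36.0% (+4.0) | 33.7% (+1.7) |
| 10/25 = 40% | 56.1% (+16.1) | 44.7% (+4.7) | 42.0% (+2.0) |
| 12/25 = 48% | 65.5% (+17.5) | 53.2% (+5.2) | 50.2% (+2.2) |

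These are averages. In the top-left cell the 5th to 95th percentiles across single trials run from 34.5% to 68.3%.

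**Step 4: a second set of timings.** 200,000 patients, 30% responders, exponential times, monthly assessment, non-responders censored at progression:

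| Median response / progression (months) | 1 − KM at 12 months | True at 12 months | 1 − KM at 24 months |
|---|---|---|---|
| 2 / 4 | 43.1% | 29.4% | 47.7% |
| 2 / 8 | 35.3% | 29.6% | 36.7% |
| 3 / 6 | 38.5% | 28.0% | 46.8% |

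The 12-month excesses are 13.7, 5.7 and 10.5 points. At 24 months the true value is about 30% (0.30 × (1 − 0.5^12) = 0.300 for a 2-month median; 0.30 × (1 − 0.5^8) = 0.299 for 3 months), so the excesses are about 17.7, 6.7 and 16.9 points.

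**Step 5: when the gap is zero.** In the Step 1 example, 1 − KM is 32.0% if no non-responder leaves before the last response, or if non-responders are kept in the risk set to the end of follow-up. In responders only, the curve reaches 100% by construction and does not estimate the probability of responding.

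**Step 6: sensitivity.** Steps 3 and 4 have responses mostly early. If instead responses continued at a constant rate per cycle, the gap would be wider. With a total event rate of 0.3 per cycle and a limiting response rate of 30%, the 12-cycle values are 29.2% (cumulative incidence) and 66.0% (1 − KM). I regard that pattern as less plausible and leave it out of the quoted range, but it shows that the range is not a bound.

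**The case against.** The strongest reply is that the sentence in Section 10.1.4 lists methods and does not specify populations. It names duration of response without restricting it to responders, yet Section 3.1 makes that endpoint meaningful only in responders. Time to response may have been meant the same way. Without censoring, Kaplan-Meier in responders is simply the empirical distribution and returns the usual median, so there would be no error. This stands: a responders-only reading is open, and so is one that keeps non-responders at risk to the end of follow-up.

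Two stronger readings are therefore unsupported. A reader might infer that the plan censors progression and death, so that the curve is bound to disagree with the response rate. The documents contain no censoring rule and no analysis set for time to response, so the bias is conditional. A reader might also infer that the primary result is in doubt. It is not: the response rate is a separate proportion with an exact interval, early progressors and deaths stay in its primary denominator, and the stage 1 rule counts responses.

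It is also fair that several of the gaps are smaller than the 10-point standard error accepted for the rate itself. That limits the priority. It does not excuse the gap, since this is a bias in one direction and the text does not exclude the biased analysis.

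**Conclusion.** The point holds in conditional form. Time to response has a named estimator but no origin, analysis set or rule for progression, death or new therapy without response. If all evaluable patients are analysed with those events censored at their dates, 1 − KM overstates the probability of response by roughly 0 to 17 points on average under the early-response timings examined. The size depends wholly on assumed response and progression times, and a single trial of 25 may fall well outside the average. Only a descriptive analysis, outside the listed objectives and endpoints, is affected. Minor priority.

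**What to change.** In Section 10.1.4 and the Protocol Summary, take time to response out of the Kaplan-Meier list and choose one option in advance:

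- **All evaluable patients.** Measure from first dose, as for PFS and OS, to first documented response that is later confirmed. Estimate by the cumulative incidence function, with progression, death or new anti-myeloma therapy before response as competing events. Censor only patients still under assessment without any of these at data cut-off. With no such censoring, the final value equals the crude response rate.
- **Confirmed responders only.** Report median and range, labelled as conditional on response.

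Keep Kaplan-Meier for duration of response, PFS and OS.

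The cost is about one sentence in each place. The dates of progression and death are already needed for the defined endpoints, and further anticancer treatment is already collected under Section 4.3. No patients, visits or data are added, and nothing in the primary analysis changes: a free improvement.

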#### 10.1.5 Safety Analysis and Stopping Rules for Excessive Toxicity

Toxicity information recorded will include the type, severity, and the probable association with the study regimen. Tables will be constructed to summarize the observed incidence by severity and type of toxicity.

The following table will be consulted as relevant toxicities are encountered. The early stopping rule for safety/toxicity will be assessed for each patient after cycle 1. The expected rate of unacceptable toxicity should not be  $\geq 33\%$ . Note: Unacceptable toxicity is defined in section 7.3 of the protocol. See the table below for detailed early stopping rules. These rules are in addition to the quarterly review of all toxicities submitted to the COH DSMC. Patients with ongoing toxicity (cycle 1 toxicity persisting beyond day +28) will be followed until resolution or stability. If more than the specified number of patients has significant treatment related toxicities, patient accrual will be halted and a full review of the data by the Data Safety Monitoring Committee (DSMC) will be mandated. Patient accrual will not resume until approved by the DSMC to do so.

# of patients treated at phase II dose	# of patients with unacceptable toxicity to halt enrollment 	Given the following toxicity rates, cumulative probability of early stopping:		
		15%	33%	45%
6	2	0.22	0.64	0.84
12	4	0.24	0.73	0.92
18	6	0.25	0.78	0.95

: For each unacceptable toxicity, halt enrollment and evaluate if the cumulative # of patients reaches or exceeds the specified limits.

We recognize that these stopping rules represent the overall stopping rules including the patient evaluated on a given dose during the Phase I portion. As such, these rules represent the stopping probabilities of a dose with the above toxicity rates, including stopping during the phase I dose finding portion. Once the MTD has been selected, and additional patients are accrued (presumably at the MTD), the probability of early stopping is less (e.g. 26% of chance of early stopping at 12 patients if the true probability of unacceptable toxicity is 33%, and a 44% chance

of early stopping at 18 patients in that scenario). This represents the probability of early stopping conditional on passing the criteria for MTD selection (0 or 1 out of 6).

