#### 7.4 Dose Escalation/Expansion

DLT incidence will be based on toxicity events encountered during the first cycle of treatment with the combination of MLN9708, pomalidomide and dexamethasone.

Dose de-escalation, escalation or cohort expansion will only take place after 3 patients are fully assessed using the Common Terminology Criteria for Adverse Events (CTCAE) of the National Cancer Institute (NCI) version 4.03 following the completion of cycle 1.

Dose escalation will occur according to the following rules:

- If zero out of 3 evaluable patients has a DLT in cycle 1 then the next dose level of combination therapy will be tested.
- If 1 out of 3 evaluable patients has a DLT in cycle 1, three additional patients will be assessed at the same dose level of combination therapy.
- If 2 out of 3 patients have a DLT in cycle 1, dose escalation will cease and the next lower dose level of combination therapy will be expanded. Note: If 2 of 3 experience DLT on dose level -1, the trial will be stopped.
- If 1 out of 6 evaluable patients has a DLT in cycle 1, then dose escalation to the next dose level of combination therapy will continue.

- If 2 or more out of 6 patients have a DLT in cycle 1, dose escalation will cease and the next lower dose level of combination therapy will be expanded. Note: If 2 of 6 experience DLT on dose level -1 the trial will be stopped.

The highest dose level that produces  $\leq 1/6$  DLTs in cycle 1 will be the maximum tolerated dose (MTD).

Note: Patients may continue therapy unless there is unacceptable toxicity, disease progression or withdrawal of consent.

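### Section 10.1.5 gives two different toxicity boundaries for halting accrual, and only the one in the table footnote reproduces the printed stopping probabilities

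*Combined protocol and SAP*

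**What the plan says.** Section 10.1.5 gives a three-row table with limits of 2, 4 and 6 at 6, 12 and 18 patients treated at the phase II dose. The column of limits is headed as the number "of patients with unacceptable toxicity to halt enrollment". The text above the table reads "If more than the specified number of patients has significant treatment related toxicities, patient accrual will be halted". It adds that a full DSMC review is then mandated and that accrual resumes only with DSMC approval. Footnote 1 says to "halt enrollment and evaluate if the cumulative # of patients reaches or exceeds the specified limits".

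Below the table the section gives the chance of stopping once a dose has been selected: "26% of chance of early stopping at 12 patients if the true probability of unacceptable toxicity is 33%, and a 44% chance" at 18 patients. It describes these figures as "conditional on passing the criteria for MTD selection (0 or 1 out of 6".

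Section 7.4 has its own phase I rule: "If 2 or more out of 6 patients have a DLT in cycle 1, dose escalation will cease". The combined file contains the protocol twice, and both copies of section 10.1.5 carry the same wording.

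**The concern.** The text sets a strict boundary (count above the limit) and the footnote an inclusive one (count at or above the limit) for the same action. With exactly 4 toxicities in 12 patients, or 6 in 18, the footnote triggers a halt and the text sentence does not. At 6 patients the question normally does not arise, because section 7.4 already rules out a dose with 2 or more of 6.

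Once the dose is selected, the 12- and 18-patient limits are the only numeric toxicity boundary left. Quarterly DSMC review and expedited reporting of serious adverse events continue, but neither carries a count. The text sentence alone attaches the mandatory DSMC review and the bar on resuming accrual, so the sentence with the operative consequence has the threshold that does not fit the table. It also names a toxicity category that the protocol does not define, where the table uses the term defined in section 7.3. That is a minor drafting point.

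**Working it through.** **Inputs**, all from section 10.1.5: looks at n = 6, 12, 18; limits 2, 4, 6; true rates p = 15%, 33%, 45%; conditioning on 0 or 1 toxicities in the first 6.

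**Rules compared**
- Inclusive (footnote): halt at ≥2, ≥4, ≥6.
- Strict (text): halt at ≥3, ≥5, ≥7.
- Mixed: the phase I rule kept at ≥2 of 6, then strict at ≥5 and ≥7.

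**Formulas.** For each block of six, b(k) = C(6,k) p^k (1−p)^(6−k), and T(r) is the sum of b(k) for k ≥ r. Paths that reach the limit are removed at each look.

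**Reproducing the plan at p = 0.33.** b(0) = 0.0905 and b(1) = 0.2673, sum 0.3578. T(2) = 0.6422, T(3) = 0.3130, T(4) = 0.0969, T(5) = 0.0170, T(6) = 0.0013. Given 0 or 1 of 6, the weights are 0.253 (none) and 0.747 (one).

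- Inclusive, by 12: 0.253 × T(4) + 0.747 × T(3) = 0.0245 + 0.2338 = **0.258**. This is the printed 26%.
- Unconditionally: 0.6422 + 0.3578 × 0.2584 = **0.735**. The table prints 0.73.
- Inclusive, by 18: the probabilities of continuing past 12 with 3, 2 or 1 toxicities are 0.3006, 0.2830 and 0.1352. The addition is 0.3006 × T(3) + 0.2830 × T(4) + 0.1352 × T(5) = 0.0941 + 0.0274 + 0.0023 = 0.124, so the total is **0.382**.
- Unconditionally: 0.6422 + 0.3578 × 0.3822 = **0.779**. The table prints 0.78.
- Strict, by 12: 0.253 × T(5) + 0.747 × T(4) = 0.0043 + 0.0724 = **0.077**.
- Strict, by 18: paths with exactly 4 of 12 (probability 0.1817) now continue. The addition is 0.1817 × T(3) + 0.3006 × T(4) + 0.2830 × T(5) + 0.1352 × T(6) = 0.0569 + 0.0291 + 0.0048 + 0.0002 = 0.091, so the total is **0.168**.

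**Unconditional probabilities at 6/12/18 patients**

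| True rate | Printed | Inclusive | Strict | Mixed |
|---|---|---|---|---|
| 15% | 0.22/0.24/0.25 | 0.2235/0.2446/0.2502 | 0.047/0.058/0.062 | 0.2235/0.2260/0.2275 |
| 33% | 0.64/0.73/0.78 | 0.6422/0.7347/0.7790 | 0.313/0.444/0.519 | 0.6422/0.6697/0.7022 |
| 45% | 0.84/0.92/0.95 | 0.8364/0.9194/0.9524 | 0.558/0.750/0.843 | 0.8364/0.8730/0.9126 |

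Inclusive matches all nine cells to two decimals. Strict matches none. Mixed matches only at 6 patients, where it is the inclusive rule.

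**Conditional on 0 or 1 of 6, by 12/18 patients**

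| True rate | Inclusive | Strict |
|---|---|---|
| 15% | 2.7%/3.4% | 0.3%/0.5% |
| 33% | 25.8%/38.2% | 7.7%/16.8% |
| 45% | 50.7%/70.9% | 22.4%/46.6% |

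At 12 patients the gap between the rules is the chance of exactly 4 of 12: 18% at a 33% rate and 28% at 45%.

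**The printed 44%.** Neither boundary gives it. Using p = 1/3 instead of 0.33 gives 39.2% inclusive and 17.4% strict, so rounding of the rate does not explain it. The table's own entries imply (0.78 − 0.64)/(1 − 0.64) = 39%.

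Section 10.1.5 has the rule assessed for each patient after cycle 1. Checking after every patient, with the limit of the current block of six, gives the same cumulative values at 6, 12 and 18.

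**The case against.** The strongest reply is that the two sentences can both be obeyed. The text does not say that accrual continues at the limit, so a site following text and footnote together halts at 4 of 12 and 6 of 18. The text also refers the reader to the table for the detailed rules, and the column heading, footnote and probabilities agree with each other. Section 11.2 gives implementation to a team that includes the statistician and meets weekly or every two weeks. Over the whole history of a dose, with the phase I rule kept, the effect at 33% is modest: 0.73 against 0.67 by 12 patients, and 0.78 against 0.70 by 18.

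Much of this stands. The intended rule can be recovered, and the halved protection describes what happens only if the text is followed alone. It remains open whether a count exactly at the limit triggers the mandatory DSMC review and the need for DSMC approval, since the footnote asks only for a halt and an evaluation.

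Two refinements also stand. Section 7.5 allows the phase II dose to be below the maximum tolerated dose. A level with fewer than six phase I patients could then meet the ambiguity at 2 of 6 in phase II, and the conditional figures would not apply. With assessment after each patient, the wordings also part when the count first equals 4 or 6 before patient 12 or 18. The 18% and 28% above are end-of-block values.

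**Conclusion.** The concern holds. Section 10.1.5 states two thresholds for one accrual halt, and its printed operating characteristics belong to the inclusive one. If the text sentence were applied on its own, the chance of halting in phase II at a 33% rate, which the section says should not be reached, would fall by more than half at both looks.

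The 44% is a separate numerical error. It overstates the conditional chance of stopping by 18 patients by about 6 percentage points (44 − 38.2) and favours neither wording.

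These figures assume independent patients with a constant toxicity rate and, for the conditional values, six phase I patients at the selected dose, as the plan expects. The point should be fixed, but it is a drafting inconsistency in a safety rule and not a flaw in the design of the boundary.

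**What to change.** Reconcile the text sentence with the table and footnote, for example: *If the cumulative number of patients with unacceptable toxicity (section 7.3) is equal to or greater than the tabulated limit, accrual is halted and full DSMC review is required.* Use the same term and the same inequality in the text, the column heading and the footnote.

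If the strict boundary was in fact intended, reword the heading and footnote and recompute the table and the 26%. With the phase I rule kept, the 33% column would read 0.64/0.67/0.70, and the conditional figures would be 8% and 17%.

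In either case recheck the 44%. Under the tabulated inclusive rule the value is 38%.

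If the inclusive rule is confirmed, the cost is one sentence and one percentage in an amendment, with no added patients or procedures.

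### The 44% chance of a toxicity stop by 18 patients (true rate 33%, after MTD selection) should be about 38%

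*Combined protocol and SAP*

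**What the plan says.** Section 10.1.5 (Safety Analysis and Stopping Rules for Excessive Toxicity) sets three looks at the phase II dose, counting the phase I patients treated at that dose. The table's footnote says enrollment halts when the cumulative count reaches or exceeds the limit. Each row gives the number treated, the limit, and the cumulative stopping probability at true rates of 15%, 33% and 45%:

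- "6 2 0.22 0.64 0.84"
- "12 4 0.24 0.73 0.92"
- "18 6 0.25 0.78 0.95"

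The text below the table explains that these probabilities include stopping during dose finding. For a dose already chosen as the MTD it gives two lower figures. The first reads "the probability of early stopping is less (e.g. 26% of chance of early stopping at 12 patients". The second, which concerns the look at 18 patients, reads "if the true probability of unacceptable toxicity is 33%, and a 44% chance". The section then defines both figures: "This represents the probability of early stopping conditional on passing the criteria for MTD selection (0 or 1 out of 6"). That condition agrees with the MTD definition in Sections 7.4 and 7.5. The same section also says that the expected rate of unacceptable toxicity should not be 33% or more.

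**The concern.** The paragraph and the table describe one rule, so the conditional figures must follow from the tabulated ones. The 26% does and the 44% does not.

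The conditional figures matter because they describe the protection left in phase II. A dose that enters with at most 1 toxicity in 6 can no longer trip the first row, so the 0.64 at 6 patients is no longer available to it. The two percentages in the text are the only conditional operating characteristics the protocol gives, and they are given at the rate it names as unacceptable. An error in the reassuring direction tells the DSMC and the IRB that the rule is more sensitive than it is.

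**Working it through.** **Inputs, all from Section 10.1.5.** Looks at 6, 12 and 18 patients; halt at counts of at least 2, 4 and 6; true rate p = 0.33; condition: 0 or 1 toxicities in the first 6.

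**Step 1: check the model against the table.** An exact binomial recursion through the three looks gives:

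| True rate | by 6 | by 12 | by 18 | Printed |
|---|---|---|---|---|
| 15% | 0.2235 | 0.2446 | 0.2502 | 0.22 / 0.24 / 0.25 |
| 33% | 0.6422 | 0.7347 | 0.7790 | 0.64 / 0.73 / 0.78 |
| 45% | 0.8364 | 0.9194 | 0.9524 | 0.84 / 0.92 / 0.95 |

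All nine entries reproduce, so this is the model behind the table.

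**Step 2: starting distribution after MTD selection.** For six patients at p = 0.33, P(0) = 0.67⁶ = 0.0905 and P(1) = 6 × 0.33 × 0.67⁵ = 0.2673, total 0.3578. The conditional weights are 0.0905/0.3578 = 0.2528 for a count of 0 and 0.2673/0.3578 = 0.7472 for a count of 1.

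**Step 3: stop at 12.** The next six patients must bring the count to at least 4. With X binomial(6, 0.33), P(X ≥ 4) = 0.0969 and P(X ≥ 3) = 0.3130.

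0.2528 × 0.0969 + 0.7472 × 0.3130 = 0.0245 + 0.2339 = **0.2584**

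The protocol's 26% reproduces.

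**Step 4: stop at 18, not having stopped at 12.** The probabilities of continuing past 12 with counts 0, 1, 2 and 3 are 0.0229, 0.1352, 0.2830 and 0.3006 (sum 0.7416 = 1 − 0.2584). To reach 6 they need at least 6, 5, 4 and 3 further toxicities, with probabilities 0.0013, 0.0170, 0.0969 and 0.3130.

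0.0229 × 0.0013 + 0.1352 × 0.0170 + 0.2830 × 0.0969 + 0.3006 × 0.3130 = 0.0000 + 0.0023 + 0.0274 + 0.0941 = 0.1238

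Cumulative by 18: 0.2584 + 0.1238 = **0.3822**, against the stated 0.44.

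**Step 5: cross-checks.**

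- From the unrounded table values: (0.7790 − 0.6422)/(1 − 0.6422) = 0.1368/0.3578 = 0.382.
- From the printed values: 0.14/0.36 = 0.389. Taking the worst rounding of each entry, the range is (0.775 − 0.645)/0.355 = 0.366 to (0.785 − 0.635)/0.365 = 0.411. The printed table therefore excludes 0.44.
- A simulation of 400,000 trials gives 25.8% and 38.2%.

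**Step 6: could another reading give both 26% and 44%?**

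| Reading | by 12 | by 18 |
|---|---|---|
| As written, p = 0.33 | 25.8% | 38.2% |
| p = 1/3 | 26.5% | 39.2% |
| p = 0.35 | 29.7% | 43.9% |
| Exactly 1 of 6, p = 0.33 | 31.3% | 44.4% |
| Extra looks at 3/9 and 5/15 | 31.0% | 43.7% |
| Halt only when the limit is exceeded | 7.7% | 16.8% |
| Single look at 18 | – | 31.1% |

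None does. Each reading that comes near 44% at 18 gives 30% or more at 12. The extra looks also fail to reproduce the table (0.75 and 0.80 instead of 0.73 and 0.78). Applying each limit continuously up to its look changes nothing, because counts only rise. Conditioning on exactly 1 of 6 may be where the 44% came from, but that is a guess, and it is not the condition the protocol states.

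**The case against.** The arithmetic cannot be defended, so the case for the plan is about weight.

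- The figure is introduced as an example. No limit, sample size, analysis or decision depends on it, and the limits and table beside it are right. This stands: what is overstated is one quoted probability, not the rule.
- The paragraph exists to warn that the stopping probability falls after MTD selection. At 44% or 38%, the reader learns that the rule more often than not fails to halt by 18 patients at a 33% rate. This is fair and limits the harm. It does not make the number right.
- Other safeguards run alongside. Section 10.1.5 adds the rule to quarterly DSMC review, and Section 11.2 has the monitoring team meet weekly or every two weeks. True, but these do not alter the rule's stated operating characteristic.
- The conditional figures apply only to a dose that has treated six patients with at most one toxicity. Section 7.5 lets the RP2D lie below the MTD, and Section 7.4 allows escalation after 0 of 3. A lower RP2D could therefore enter phase II with three patients, and the 2-of-6 limit could still bind. This stands as a limit on scope. It applies equally to the 26%, the 44% and the corrected 38%.
- Section 10.1.5 also uses wording that would halt only when the specified number is exceeded. That reading moves the answer further from 44% (16.8%) and does not reproduce the 26%.

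**Conclusion.** The 44% is wrong as written. Under the protocol's own limits, true rate and stated condition, the chance of a toxicity stop by 18 patients is 38.2% (39.2% if 33% is read as one third). The overstatement is 44 − 38.2 = 5.8 percentage points, in the reassuring direction. The companion 26% and all nine table entries are correct.

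The result assumes independent patients with a common toxicity rate, the reach-or-exceed footnote, and six patients already treated at the dose with at most one toxicity. The first two assumptions are those that reproduce the table, and the third is the condition the section itself states. The error is small and changes no rule. It should still be corrected, because it misstates how the safety rule performs in the scenario the protocol singles out.

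**What to change.** In Section 10.1.5, replace 44% with 38%, in both places where the section appears in the combined document. The cost is one number; the stopping limits, table, sample size and conduct do not change.

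Optionally, add the conditional probabilities by 12 and by 18 patients next to the table: 2.7% and 3.4% at a true rate of 15%, 26% and 38% at 33%, and 51% and 71% at 45%. A note should say that they apply when six patients have already been treated at the dose with at most one toxicity.
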